Random assignment will be performed centrally, using a computer-based central randomization system integrated in a Web-based electronic case-report form (REDCap) to guarantee adequate allocation concealment. Random assignments will be stratified by center, presence or absence of baseline SIRS, and presence or absence of baseline hypovolemia. Permuted 12-patients blocks will be used.

Sample Size (R11)

The WATERFALL trial had a frequency of moderately severe or severe AP in the moderate fluid resuscitation arm of treatment (based on LR) of 17%. (14) In a recent systematic review, patients who received LR-based fluid resuscitation were less likely to develop moderately severe or severe pancreatitis than patients receiving NS, with an OR of 0.49, 95 % CI 0.25-0.97. (23) The differences in the incidence of moderately severe or severe pancreatitis in the four included randomized controlled trials between LR and NS ranged from 10 to 14% favoring LR. (23) For this reason, we expect an incidence of moderately severe or severe AP in the NS arm of 27%. Patients will be assigned in a 1:1 ratio. A total sample of 720 patients, 360 in the LR group and 360 in the NS group, will achieve 90% power to detect a difference between the group proportions of 10% (smaller difference observed in the 4 RTCs (23)), assuming that the frequency of moderately severe or severe AP in LR group will be 17%. The frequency in the NS group is assumed to be 17% under the null hypothesis and 27% under the alternative hypothesis. A loss to follow-up of 10% of patients is expected, so the sample size will be 396 patients in each treatment arm (792 patients in total). The test statistic used is the two-sided Z test with pooled variance set at a 0.05 significance level.

Framework (R12)

The WATERLAND trial is a superiority trial.

Statistical Interim Analyses and Subgrouping Guidance.

Information on interim analyses specifying what interim analyses will be carried out and listing of time points (R13a)

Given that NS and LR are both commonly used and effective IV fluids for resuscitation and generally safe and well tolerated, no interim analysis has been predefined. The Data and Safety Monitoring Committee will evaluate all reported adverse events. Safety reports will be issued as reported and analyzed by the Steering Committee.

Any planned adjustment of the significance level due to interim analysis (R13b)

Not applicable.

Details of guidelines for stopping the trial early (R13c)

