Patients will be described for age, sex assigned at birth, first episode of pancreatitis, gallstone cause of pancreatitis, body-mass index, Charlson comorbidity index, BISAP score, HAPS score, PAN-PROMISE score, urea, hematocrit, creatinine, SIRS, hypovolemia, potassium, calcium, pH, and chlorine, both overall and separately for the two randomized groups. The representativeness of the study participants will be discussed in another table in the supplementary material containing information about

the disease studied, special considerations about sex and gender, age, race, geography, other considerations, and the overall representativeness of this trial. (25)

Details of how baseline characteristics will be descriptively summarized (R25b)

Categorical data will be summarized by numbers and percentages. Continuous data will be summarized by mean and SD if data are normal and median and interquartile range if data are skewed. Tests of statistical significance will not be undertaken for baseline characteristics; instead, the clinical importance of any imbalance will be noted.

Section 6: Analysis

Outcome Definitions

Specification of outcomes and timings (R26a), specific measurement and units (R26b), and any calculation or transformation used to derive the outcome (R26c)

The specifications on outcomes and timings, specific measurements and units, and calculations used to derive outcomes are explained in the study protocol (main text: "Outcomes," and Tables 2, 3, and 4). To calculate the change from the baseline PAN-PROMISE scale at 24 and 48 hours, we will subtract the baseline value from the values at those time points. In addition, we will analyze the data at 24 and 48 hours, considering both baseline-adjusted and non-adjusted values.

Analysis methods

What analysis method will be used, and how the treatment effects will be presented (R27a)

Normality will be assessed using the Lilliefors-corrected Kolmogorov-Smirnov test. The number and percentage of primary and secondary categorical outcomes will be reported for each treatment group. Continuous data will be reported by mean and SD if data are normal and median and interquartile range if data are skewed.

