To calculate the p-value for the primary outcome and secondary safety outcomes, the Cochran–Mantel–Haenszel method will be utilized, with adjustments made for randomization stratification factors including center, baseline SIRS presence, and baseline hypovolemia presence. In addition, this procedure will yield adjusted relative risks and their corresponding 95% confidence intervals for all outcomes, also accounting

for any variables that display imbalances among randomized groups. For continuous variables, adjusted relative risks will be calculated using multiple regression models adjusted for randomization stratification factors and any variable that display imbalances among randomized groups to analyze the effect of the continuous variable itself. Additionally, the Cochran-Mantel-Haenszel method will be applied to compare high values (above the median) to low values (at or below the median), providing a comprehensive analysis of the data

Any adjustment for covariates (R27b)

As explained in R27a, p-values and relative risk will be adjusted for randomization stratification factors (center, baseline presence or absence of SIRS, and baseline presence or absence of hypovolemia). Additionally, adjustments may also include variables that exhibit imbalances across randomized groups.

Methods used for assumptions to be checked for statistical methods (R27c)

The Lilliefors-corrected Kolmogorov-Smirnov test will be used to assess the normality of continuous data. We will also assess the assumptions of the regression models used in the data analysis

Details of alternative methods to be used if distributional assumptions do not hold (R27d)

If continuous variables do not adhere to normal distribution assumptions, alternative methods such as variable transformations, robust regression techniques, or bootstrap methods will be considered. Similarly, if regression models do not meet assumptions, non-parametric models or robust models will be explored to ensure robustness of the findings.

Any planned sensitivity analyses for each outcome where applicable (R27e)

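### The primary analysis pre-specifies only center, SIRS and hypovolemia; recorded prognostic scores can enter only if judged imbalanced, so their precision is not secured

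*Combined protocol and SAP*

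**What the plan says.** Three parts of the SAP bear on this point.

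- **Method and adjustment set.** R27a: "To calculate the p-value for the primary outcome and secondary safety outcomes, the Cochran–Mantel–Haenszel method will be utilized", adjusting for the three randomization factors. R27b: "p-values and relative risk will be adjusted for randomization stratification factors", listing center, SIRS and hypovolemia. Protocol item {20a} describes the same analysis.
- **Other variables.** R27b continues: "Additionally, adjustments may also include variables that exhibit imbalances across randomized groups". R27a attaches a similar provision to the relative risks, but its sentence on the p-value names only the stratification factors. The trigger is described in R25b: "Tests of statistical significance will not be undertaken for baseline characteristics; instead, the clinical importance of any imbalance will be noted". No threshold is given.
- **What is recorded.** R25a lists age and, among others, "Charlson comorbidity index, BISAP score, HAPS score, PAN-PROMISE score, urea, hematocrit, creatinine, SIRS, hypovolemia" as characteristics to be described. No sentence enters any of the scores because it predicts the outcome.

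The sample size (R11) uses no covariates: "The test statistic used is the two-sided Z test with pooled variance set at a 0.05 significance level".

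**The concern.** A baseline variable that predicts moderately severe or severe pancreatitis sharpens the treatment comparison whether or not it happens to be imbalanced. The plan makes imbalance the condition for using such a variable, leaves its use optional, and has the decision made after the data are seen. The trial recruits both predicted mild and predicted severe disease (protocol, Discussion), so baseline risk should vary, and two binary stratifiers capture that variation coarsely.

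At stake is the width of the confidence interval and the power obtained from patients already enrolled. The scores are already collected, so using them needs no new data, but it does need a different method of analysis.

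**Working it through.** **1. The plan's own figure.** Inputs from R11: 17% (LR) versus 27% (NS), two-sided 0.05, pooled Z test, 1:1 allocation, 90% power. The mean proportion is 0.22.

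n per arm = [1.960 × √(2 × 0.22 × 0.78) + 1.2816 × √(0.17 × 0.83 + 0.27 × 0.73)]² / 0.10² = [1.1482 + 0.7453]² / 0.01 = 358.5, so 359. The plan's 360 reproduces.

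Power at 360 = Φ[(0.10 × √360 − 1.1482) / 0.5816] = Φ(1.288) = 90.1%.

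**2. Gain from a covariate, by formula.** Let R² be the share of outcome variance that a score explains beyond the existing factors. The documents give no value, so a range is assumed. Effective n per arm is 360/(1 − R²), the standard error is multiplied by √(1 − R²), and the n giving the original power is 360 × (1 − R²).

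| Assumed R² | Power at 360 per arm | SE multiplier | n per arm for the original power |
|---|---|---|---|
| 0 | 90.12% | 1.000 | 360 |
| 0.02 | 90.68% | 0.990 | 353 |
| 0.05 | 91.51% | 0.975 | 342 |
| 0.10 | 92.85% | 0.949 | 324 |
| 0.15 | 94.11% | 0.922 | 306 |

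The gain is therefore about 0.6 to 4.0 points.

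**3. Separating the score from the method.** The formula ignores the stratified test, so trials were simulated: 720 patients, blocks of 12 within center × SIRS × hypovolemia, 1,500 trials per row. All of the following are assumptions: unequal center sizes, SIRS 30% and hypovolemia 40% (log odds ratios 0.8 and 0.4), center SD 0.4 on the logit scale, and a score with log odds ratio 0.3, 0.6 or 0.9 per SD (AUC about 0.58, 0.65, 0.71), independent of SIRS and hypovolemia. The regression is linear with robust standard errors and has no center term. Power in %:

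| Centers | Score AUC | Unadjusted | Planned CMH (center × SIRS × hypovolemia) | Planned CMH with score as extra stratum | CMH on SIRS and hypovolemia | Regression on SIRS, hypovolemia and score |
|---|---|---|---|---|---|---|
| 20 | 0.58 | 89.9 | 89.1 | 87.0 | 89.7 | 90.3 |
| 20 | 0.65 | 89.0 | 87.7 | 86.6 | 89.7 | 91.4 |
| 20 | 0.71 | 89.5 | 88.3 | 87.3 | 90.0 | 92.5 |
| 40 | 0.58 | 91.4 | 89.1 | 82.9 | 92.0 | 92.3 |
| 40 | 0.65 | 89.8 | 85.9 | 81.0 | 90.1 | 91.6 |
| 40 | 0.71 | 90.7 | 88.3 | 86.3 | 91.3 | 93.3 |
| 60 | 0.58 | 91.7 | 86.1 | 77.0 | 92.2 | 92.9 |
| 60 | 0.65 | 90.1 | 84.9 | 78.1 | 91.1 | 92.5 |
| 60 | 0.71 | 89.3 | 83.8 | 78.5 | 89.7 | 93.0 |

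The Monte Carlo SE of one entry is about √(0.9 × 0.1/1500) = 0.8 points.

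- Leaving the fully crossed strata (fourth to sixth column) gains 0.6 to 2.0 points with 20 centers, 2.9 to 4.2 with 40 and 5.9 to 6.2 with 60.
- Going on to the regression with the score (sixth to seventh column) gains 0.3 to 3.3 points. Adding the score to the regression shortens the SE by about 0.6%, 2.5% and 5% at the three strengths.
- Adding the score as one more CMH stratum lowers power in every row.
- Under the null (40 centers, AUC 0.65), all methods rejected in 5.1 to 5.7% of trials (Monte Carlo SE about 0.6 points).

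**4. The model form recommended below.** A separate simulation (800 trials per cell; 20 or 40 centers; same SIRS and hypovolemia prevalence; log odds ratio 0.3 to 0.9 per SD) used logistic regression with standardization. Power was 83–91% for the planned CMH, 88–92% for the model without the score and 89–94% with it. The score added about 0 to 5 points, and type I error was near 5%.

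**5. Center terms.** A further simulation (1,000 trials per cell) put center terms in the model together with the score. Power was 91–95%, but null rejection ran from 4.6 to 7.1% (Monte Carlo SE about 0.7 points), highest at 40 centers.

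**The case against.** The strongest reply is that the planned test is valid, meets its power target on its own inputs, and that choosing another valid test is a matter of preference. Its parts differ in weight.

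- A reader might infer that the scores are shut out of the analysis. They are not: the imbalance clause lets them in. It does so optionally and without a threshold, and imbalance is not what determines the precision gain.
- A reader might infer that adjustment is free. It is free in data collection only. Within CMH the scores would split strata that are already thin and cost power, so the gain requires a change of primary method. R27a names regression for continuous variables, not for this binary outcome.
- A reader might infer that the trial is underpowered. The documents do not support that. The target is met at 360 per arm, and the pooled Z test gives 92.6% if all 396 per arm are analysed. If a full 10% are lost, 396 × 0.90 = 356 remain and power is 89.8%, which is still essentially the target. The planned CMH's lower simulated power depends on an assumed number of centers.
- The gain may be near the bottom of the range. Patients who already meet criteria for moderately severe or severe disease are excluded (protocol, Discussion), which narrows the spread of severity, and SIRS may already carry some of the same information.
- A late change to the primary test of an open-label trial has a credibility cost. Protocol item {25} says that changes from the protocol will be labelled post hoc.

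All of these limit the point, and the last is a real cost. None of them secures the unused precision.

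**Conclusion.** The point holds as one of efficiency. The plan fixes three adjustment factors and leaves prognostic variables already in hand to an optional trigger that depends on observed imbalance. No bias, invalid test or failure of the stated sample size follows from this.

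The total gain should not be credited to the scores alone. A score contributes about 0 to 5 points of power. Leaving the sparse crossed strata contributes up to about 5 points at 20 or 40 centers and about 6 in the 60-center rows. These figures rest on assumed score strength, number and size of centers, and prevalence of SIRS and hypovolemia, none of which the protocol or SAP supplies. The direction is secure if at least one recorded score is prognostic beyond SIRS and hypovolemia; the size is not.

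**What to change.** Before the analysts learn which arm is A and which is B, amend R27a and R27b, and protocol item {20a} to match:

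1. Name one or two baseline covariates, for example BISAP and either the Charlson index or age, entered whatever their balance. State that the imbalance clause does not alter this primary model.
2. Take the primary p-value and the relative risk from one logistic model with arm, SIRS, hypovolemia and the named covariates, with the relative risk and its 95% CI obtained by standardization.
3. State how small centers are pooled or modelled, because many fixed center terms may inflate type I error.
4. Give a simple rule for missing baseline scores; the documents give no expected rate of missingness.
5. Keep CMH as a supporting analysis, and do not add the scores to it as strata.

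The change needs no new data or patients. Its costs are that the primary result becomes model-based and that the amendment must be dated and documented as made before the analysts were unblinded, given the labelling rule in item {25}.
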